**Table 1.**  
**O2 WEANING PARAMETERS**

	STANDARD OXYGEN MANAGEMENT ARM	CpOx OXYGEN MANAGEMENT ARM
CRITERIA FOR INCREASING O2 FLOW RATE	INABILITY TO MAINTAIN O2 SAT >93% AT PATIENT'S CURRENT O2 LEVEL FOR 20 MINUTES IN CLINIC VISIT CHALLENGE	INABILITY TO MAINTAIN O2 SAT >93% FOR >95% OF RECORDED TIME
CRITERIA FOR MAINTAINING CURRENT O2 FLOW RATE	ABILITY TO MAINTAIN O2 SAT >93% AT PATIENT'S CURRENT O2 BUT UNABLE TO MAINTAIN O2 SAT >93% AT WEANED FLOW RATE FOR 20 MINUTES IN CLINIC VISIT CHALLENGE	ABILITY TO MAINTAIN O2 SAT >93% FOR >=95% OF RECORDED TIME BUT UNABLE TO MAINTAIN O2 SAT >96% FOR >=95% OF RECORDED TIME
CRITERIA FOR WEANING O2 FLOW RATE	ABILITY TO MAINTAIN O2 SAT >96% AT WEANED FLOW RATE FOR 20 MINUTES IN CLINIC VISIT CHALLENGE	ABILITY TO MAINTAIN O2 SAT > 96% FOR >=95% OF RECORDED TIME

\* Clinic pass and fail will be determined per clinic assessment of oximeter alarms.

\*\* CpOx pass and fail will be determined by assessment of recorded oximetry. A minimum of 4 days of data, with a minimum of 8 hours per day, will be required for analysis to make any wean.

For infants in both arms, O2 weaning will proceed, when allowable per weaning criteria in the protocol, in 50% increments to a minimum of 125 cc/min. (For example, flow rate of 500 cc/min will be decreased to 250 cc/min, and 250 cc/min will be decreased to 125 cc/min.) Once infants achieve flow rates of 125 cc/min (or if they are discharged home from NICU on <125 cc/min), the next weaning step will be to room air during the day and nocturnal O2 only at a flow rate of 125 cc/min.

When infants in arm A have weaned to the final stage before discontinuation (O2 flow rate <= 125 cc/min, utilized only at night), they will be scheduled for an overnight polysomnography (PSG). These infants will have overnight recording with the Masimo Rad-8 pulse oximeter and serial data recorder on the nights prior to and during the PSG. Final decision regarding safe discontinuation of supplemental O2 therapy will be based on O2 saturation and growth outcomes; infants who do not meet criteria on the first PSG will remain on overnight O2 supplementation and repeat the PSG monthly until they pass.

To determine “Pass” of PSG or to determine ability to wean versus hold on current therapy versus escalate support, strict protocols to analyze O2 saturation status will be followed:

**For patients randomized to standard therapy weaning:**

Clinic staff will monitor the patient for 20-minute intervals to determine whether infants maintain saturations above the target saturation limits defined in Table 1 to determine whether weaning can proceed at that visit.

**For patients randomized to HRO-based weaning:**

We will determine the number of seconds/hour with saturation >96, < 93, and < 90%, and the percentage of time below these thresholds for each recording interval (minimum 4-day epochs during weaning for

randomized infants, and 12 hour epochs for all infants both on the night before and during PSG) using target saturation limits defined in Table 1 to determine whether weaning can proceed.

**For PSG evaluations:**

Infants will “pass” the PSG when they can maintain O2 saturation >93% for >95% of the time, with a minimum of 8 hours of nocturnal recording.

**Control for Confounding Variables**

Although this is a randomized trial, to account for potential confounding factors, we will extract demographic and NICU clinical variables. All clinical sites will complete a data collection form using a secure web portal. Family demographic data will include history of any fetal exposures (including smoking, alcohol, street drugs), parental ages and highest education levels achieved, marital status and other environmental or home influences affecting infant development. Infant data will include time to full oral feeds, breast feeding status at discharge and at home, and all diagnoses at enrollment, hospital discharge, and to study completion, including PDA ligation, and any documented fungal/bacterial sepsis or meningitis, and bronchopulmonary dysplasia or chronic lung disease. The severity-of-illness data collected will include last day of (1) intubation, (2) nasal continuous positive airway pressure, (3) high flow (>2 L) and low flow nasal cannula use, and (4) supplemental O2. Weight, length and head circumference at birth, hospital discharge, and first clinic visit will be recorded. Other medications recorded will include postnatal steroids, and all prescribed medications at home.

**g. Study Timeline (as applicable)**

We expect to enroll the total of 68 patients from BCH over a 3.5-year period. (This is a multicenter study. Total enrollment will be 196 infants. We anticipate that our final patients will complete oxygen weaning after 6 months and 6-month follow-up for final outcomes assessment will be within 3 years of starting this project.

**h. Adverse Event Criteria and Reporting Procedures**

Information about all adverse events, whether volunteered by the subject, discovered by investigator questioning, or detected through physical examination, or other means, will be collected and recorded and followed as appropriate.

An adverse event is the appearance or worsening of any undesirable sign, symptom, or medical condition occurring after starting the study intervention even if the event is not considered to be related to study intervention. The occurrence of adverse events should be sought by non-directive questioning of the patient at each visit during the study. Adverse events also may be detected when they are volunteered by the patient during or between visits or through physical examination, or other assessments. As far as possible, each adverse event should be evaluated to determine:

1. the severity grade (mild, moderate, severe) or (grade 1-4)
2. its relationship to the study device(s) (suspected/not suspected)
3. its duration (start and end dates or if continuing at final exam)
4. whether it constitutes a serious adverse event (SAE)

All adverse events should be treated appropriately. Such treatment may include changes in study treatment including possible interruption or discontinuation, starting or stopping concomitant treatments, changes in the frequency or nature of assessments, hospitalization, or any other medically required intervention. Once an adverse event is detected, it should be followed until its resolution, and assessment should be made at each visit (or more frequently, if necessary) of any changes in severity, the suspected relationship to the study intervention, the interventions required to treat it, and the outcome. The IRB at

each site will be notified about adverse events in compliance with its policy of safety reporting. ( e.g. according to BCH IRB policies, all adverse events that do not qualify the definition of an “reportable” event will be notified at the yearly continuing review).

**Serious Adverse Events (SAE):**

A serious adverse event is an undesirable sign, symptom or medical condition which:

- is fatal or life-threatening
  - Non-infectious hypoxic events or Acute Life Threatening Events (ALTEs) between and during monthly clinic visits
  - Development of newly diagnosed pulmonary hypertension.

OR

- results in persistent or significant disability/incapacity

OR

- requires inpatient hospitalization or prolongation of existing hospitalization, unless hospitalization is for one of the following:
  - routine treatment or monitoring of the studied indication, not associated with any deterioration in condition
  - elective or pre-planned treatment for a pre-existing condition that is unrelated to the indication under study and has not worsened since the start of study drug
  - treatment on an emergency outpatient basis for an event not fulfilling any of the definitions of a SAE given above and not resulting in hospital admission
  - social reasons and respite care in the absence of any deterioration in the patient's general condition

OR

- is medically significant, i.e., defined as an event that jeopardizes the patient or may require medical or surgical intervention to prevent one of the outcomes listed above

**SAE Reporting:** Information about all serious adverse events will be collected and recorded. To ensure patient safety, each serious adverse event must also be reported to the PI as soon as possible after learning of its occurrence

At BCH, according to its IRB policies, Serious Adverse Events that are **serious, unexpected and related** to the study, including rehospitalizations and emergency department visits will be reported to the study's DSMB and IRB promptly (within 72 hours of occurrence). At all other sites, the SAE reporting will comply to the site specific IRB policies. New diagnoses of pulmonary hypertension will similarly be reported to the DSMB and IRB within 72 hours of diagnosis. All Adverse events and Serious Adverse events will be presented to the DSMB board every 6 months.

i. **If the Investigator is the Sponsor/Assignee (IND or IDE-holder), he/she is responsible for selecting a qualified monitor who will monitor the progress of all clinical investigations conducted under the IND or IDE. Please describe the monitoring plan for this protocol below:**

↳ Note: the EQuIP office provides monitoring services and advice. For info, contact EQuIP @ [name].

Not applicable

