## **4. Design and Methods**

### ***4a. Study Design***

We plan a prospective, multicenter, randomized trial of premature infants who require HOT. We will follow infants, beginning at the time of their first outpatient pediatric pulmonary appointment and continuing until 6 months from discontinuation of HOT. Duration of HOT therapy for each arm of the study will be documented by each site investigator. Questionnaires throughout the HOT managing process and after oxygen discontinuation will assess the impact of each HOT managing process on the parent quality of life. Growth assessments throughout of the HOT managing process and after oxygen discontinuation will track safety of both protocols. Similarly, assessment of health-care utilization (respiratory-related emergency department visits or rehospitalizations) at 6 months after discontinuation of HOT will track safety as well.

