Although our primary outcomes focus on quality of life, the secondary outcomes were chosen to confirm that weaning strategies (that likely improve quality of life) are not less safe. Assessment of short-term outcomes after discontinuation of therapies may miss significant later morbidities. We therefore included clinically relevant secondary outcomes at 6 months post discontinuation of O2 to assess the safety of the weaning strategies. Inadequate O2 supplementation has been associated with poor somatic growth, so growth parameters are an important outcome to confirm long-term safety of all studied weaning protocols. Higher O2 target saturations, with subsequent increased exposure to supplemental O2, have been linked to increased numbers of respiratory exacerbations. We therefore are also including rates of respiratory-related emergency department visits and rehospitalizations as additional secondary outcomes.

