**- Monthly Visits: ( ARM A and ARM B): (V1 onwards until wean)**

1. Parents will be asked to complete the PedsQL at follow-up monthly clinic visits until the infant is weaned. In case the PedsQL is not obtained during the clinic visit, due to time constraints, these surveys can be conducted over the phone in the privacy of their home. This is to ensure we have consistent data on all patients in our study.
2. Growth parameters (WHO) and nutrition notes will be obtained at all monthly visits (prior to weaning).

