**f. Data and Safety Monitoring Plan**

A Data Safety and Monitoring Board (DSMB) will provide oversight for this study. The DSMB will be constituted to oversee the safety of patients on this trial. The DSMB will meet after the first 8 patients have been enrolled, and subsequently not less than twice yearly. The DSMB will include 2 neonatologists (not associated with the study) and two pediatric pulmonologists (not associated with the study) as well as one primary pediatrician from the community (also not associated with the study). We will also include a member of our Parent Advisory Board, a parent of a premature infant who had required oxygen supplementation in the home in the past.

At the beginning of each meeting, [name] and the primary research coordinator will be present to discuss study enrollment and any issues, and then they will leave the meeting so the DSMB can review

any adverse events. If one of the arms is noted to have more than 3 respiratory re-hospitalizations, the committee will come together and decide what, if any part of the study needs to be altered and/or stopped.

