**Stopping Rules:**

The study will be stopped, if there are least 3 *related* respiratory related hospitalizations in one arm *and* the majority of the DSMB votes that these are study related and cannot be remedied.

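### Growth is given a safety role and measured monthly, but no by-arm growth data are scheduled for the DSMB during enrolment

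*Combined protocol and SAP*

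**What the plan says.** **Role of growth.** Section 4a (Study Design) states: "Growth assessments throughout of the HOT managing process and after oxygen discontinuation will track safety of both protocols". Section 4e reports that inadequate oxygen supplementation has been associated with poor somatic growth, and concludes that "growth parameters are an important outcome to confirm long-term safety of all studied weaning protocols". It names respiratory emergency visits and rehospitalisations as further safety outcomes.

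**Measurement.** The Monthly Visits paragraph of Section 4f says: "Growth parameters (WHO) and nutrition notes will be obtained at all monthly visits (prior to weaning"). The Post Wean Follow-Up paragraph adds growth at 1 and 6 months after weaning. Section 4d is broader and places growth at monthly clinic visits both before and after the wean.

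**What the board receives.** Under Serious Adverse Events: "All Adverse events and Serious Adverse events will be presented to the DSMB board every 6 months". On meetings, Section 5f says: "The DSMB will meet after the first 8 patients have been enrolled, and subsequently not less than twice yearly". Study staff first discuss enrolment and any issues, "then they will leave the meeting so the DSMB can review" adverse events. The discussion trigger is worded "any adverse events. If one of the arms is noted to have more than 3 respiratory re-hospitalizations". The Stopping Rules paragraph counts related "respiratory related hospitalizations in one arm" and also requires a majority vote of the board.

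**The concern.** The protocol names two kinds of safety outcome in Section 4e: hospital and emergency use, and growth. The first reaches the board on a schedule and has a trigger. The second has neither.

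This matters because the RHO arm may have oxygen reduced between monthly visits, and the plan anticipates a 25% shorter oxygen course. If that proves too short for some infants, the protocol's own reasoning points to poorer growth as one consequence. Part of that could be a shift in the arm's average with no single infant standing out. The DSMB is the body that can alter or stop the study, and as written nothing puts such a shift in front of it while infants are still being randomised.

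**Working it through.** **1. Can growth reach the board by any written route?** The provisions, side by side:

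- Six-monthly report (Serious Adverse Events): adverse events and SAEs. Growth is not named.
- Meetings (Section 5f): enrolment, any issues, adverse events. Growth is not named.
- Trigger (Section 5f) and Stopping Rules: respiratory hospitalisations only.
- Adverse event definition (Section 4h): broad, covering the worsening of any undesirable sign, including one found on examination. One infant's faltering growth could qualify. No growth threshold is given, and events are to be sought by non-directive questioning.
- Growth in the decision to stop oxygen: mentioned in the text after Table 1, in the paragraph on Arm A's polysomnogram. This concerns the individual infant and is not a comparison of arms.
- Analysis plan (Sections 5c and 5d): the Aim 3 hypothesis mentions growth, but no method, timing, margin or power is given for it.

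So there is an individual route that depends on investigator judgement, and no scheduled arm-level route.

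**2. How much could a by-arm table show?** The plan gives no growth SD, margin or power, so there is no figure of its own to reproduce. What follows is illustrative.

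Inputs from the documents: 98 infants per arm; 3.5 years of accrual (stated for the BCH patients); mean HOT duration of 144 days in the standard arm; growth endpoint 6 months after discontinuation.

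Assumptions: the 3.5 years applies to the whole trial with uniform accrual; SD of change in weight z-score 0.8 to 1.2; a true deficit of 0.5 z.

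*Infants available at half enrolment*

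- Accrual: 98 / 3.5 = 28 per arm per year, so half enrolment (49 per arm) falls at 1.75 years.
- Time to the endpoint: 144 days + about 182.5 days = 326.5 days, or 0.894 years.
- With the full endpoint: 28 × (1.75 − 0.894) ≈ 24 per arm, before dropout.

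*Precision*, with SE = SD × √(2/n):

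| n per arm | SD | SE | 0.5 / SE |
|---|---|---|---|
| 24 | 0.8 | 0.231 | 2.2 |
| 24 | 1.0 | 0.289 | 1.7 |
| 24 | 1.2 | 0.346 | 1.4 |
| 49 | 0.8 | 0.162 | 3.1 |
| 49 | 1.0 | 0.202 | 2.5 |
| 49 | 1.2 | 0.242 | 2.1 |

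The n = 49 rows are an upper bound, since recently enrolled infants have little or no change to contribute. Even there, the 95% half-width (1.96 × SE) is 0.32 to 0.48 z, and a single two-sided 5% comparison has 54% to 87% power for 0.5 z.

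*A smaller deficit.* For 0.2 z at n = 49, the ratio is 0.2 / 0.242 = 0.8 to 0.2 / 0.162 = 1.2 standard errors. The table would not separate that from chance.

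*Sensitivity to accrual.* The Study Timeline also places final outcomes within 3 years of the start. Taking off about 6 months for weaning and 6 months for follow-up leaves 2 years of accrual, or 98 / 2 = 49 per arm per year. At half enrolment (1 year) only about 49 × (1 − 0.894) ≈ 5 per arm would have the full endpoint. A table limited to that endpoint would then be nearly empty, which is why the monthly measurements should be used.

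**The case against.** The strongest reply is that the board is less blind than the report contents suggest. Its charge is to oversee patient safety, the meeting covers any issues, and it can ask for growth data. Faltering growth in one infant can be an adverse event. Severe consequences of low oxygen, such as hypoxic events, acute life-threatening events and new pulmonary hypertension, are listed as SAEs. In the RHO arm oxygenation is recorded directly every 4 to 7 days, and Table 1 has criteria for increasing flow. All of this stands. A reader might infer that growth harm cannot be seen at all, and the documents do not support that.

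Two other stronger readings also fail. One is that growth is the protocol's designated marker of inadequate oxygen: Section 4e states an association and lists growth beside respiratory outcomes. The other is that growth will first be compared by arm at the end of the trial: the plan gives no timing for that comparison, so this would be inference from silence and from the endpoint definition.

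The second line of reply is that a by-arm table could mislead. After weaning, the Post Wean paragraph schedules growth only at 1 and 6 months. RHO infants are expected to wean sooner (108 against 144 days), so later months may be missing unevenly between arms, with infants still on oxygen over-represented. Repeated looks also bring some risk of a false alarm. These points limit how the table should be built and read, but do not remove the case for it. Section 4d provides for growth at monthly visits after the wean as well, and showing the numbers measured and missing lets the board judge the imbalance.

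None of the safeguards above compares growth between arms. Section 5f lists clinicians and a parent but no statistician on the board, so a pre-specified table is more dependable than waiting for a request.

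**Conclusion.** The point holds as a gap in scheduled oversight. Growth has a stated safety role and is measured monthly, but no by-arm growth data are scheduled for the DSMB, and neither the trigger nor the stopping rule uses growth. An arm-level shift therefore has no planned review during enrolment. This is an inexpensive improvement to monitoring; it does not make any planned analysis invalid.

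A reader might take a half-enrolment look to place a 0.5 z deficit firmly at 2 to 3 standard errors. That would require all 49 infants per arm to have full change data, which the follow-up schedule rules out. With about 24 per arm the figure is 1.4 to 2.2. All of these figures rest on an assumed SD, an assumed deficit and an assumed trial-wide accrual period. They support only the statement that a table could reveal a large deficit and would probably miss a small one.

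**What to change.** Amend the six-monthly reporting sentence under Serious Adverse Events along these lines: *Every six months the DSMB will receive (a) all adverse and serious adverse events and (b) a descriptive table, by randomised arm, of change in weight z-score and weight-for-length z-score since the first clinic visit.*

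Specify that the table:

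- uses matched months since randomisation;
- includes every randomised infant with an available measurement, whether or not weaned;
- shows the number measured and the number missing in each arm at each month.

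The text should describe the table as descriptive, given the uneven missingness and repeated looks. The post-wean growth schedules in Section 4d and the Post Wean Follow-Up paragraph should be reconciled, so that it is clear which measurements the table can expect. No new trigger or clinical rule is needed, because Section 5f already lets the board consider altering or stopping the study.

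The cost is a little programming for a report already due twice a year, from data already collected, plus some risk of a false alarm. It adds no visits and no look at the efficacy outcomes.

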## **5. Data Management and Statistical Analysis**

### **a. Data Management Methods**

Subjects will be provided with a unique ID code and only the study coordinator, Principal Investigator and study monitor will be able to view the link between participants' names and the unique ID. The link to all codes will be maintained in a secure, HIPAA compliant database in the study coordinator's office. The unique patient number will be used on all research documents, including case report forms, as well as on labels on samples collected. All information from this study will be kept in the same research binder in the study coordinator's private and locked office at UMass Medical Center. This will include all paperwork with identifying information, including tracking sheets, orders, consents, etc. After each clinic visit, the BCH study staff will transfer all essential documents including clinic notes, anthropometrics and study surveys to the research team based at UMass using secure file transfer methods.

Pre-enrollment/screening clinical and laboratory data may be collected by study staff from the medical record. Case report forms (CRFs) will be designed for collection of all clinical and laboratory data with input from the BCH Clinical Research Center (CRC) staff and statistician. The CRC staff includes experienced data managers who will be responsible for creating the data base and training study staff at all sites in data entry into the data base. The data manager will work with the study statistician to ensure that all appropriate measures are collected and coded correctly. The clinical research coordinator will work with study and coordinate with the site study monitor to ensure data quality and integrity.

The CRC clinical research staff provides data management expertise for many clinical trials that take place at Boston Children's Hospital. Data will be collected by the research coordinator who has been trained in how to collect the specific clinical and laboratory data from the medical record. All data will subsequently be entered into the electronic database created specifically for this study using RedCap. The database will be designed with rules to prevent entry of impossible values for relevant fields. Subjects will be identified only by a study identification number in the database. The database will be password protected with a password known only to study staff, who need to enter or access data. Files with the study ID number linked to the subjects' actual names and hospital medical record numbers will be kept separately by the site PI at each site.

The CRC representative will review the data entered in the eCRFs for completeness and accuracy and instruct the site team to make any required corrections or additions. Queries will be generated and sent to the site team using an electronic data query. Designated site team personnel will respond to the query and confirm or correct the data. Concomitant medications entered in the database will be coded using the WHO drug reference list. Adverse events will be coded using the medical dictionary for regulatory activities (CTCAE Coding) terminology.

